3.5 Quality of Life Questionnaire

Quality of life will be captured using the Atrial Fibrillation Effect on Quality of Life (AFEQT) questionnaire. It is a standardized, disease-specific, reliable and responsive measure of health-related quality of life in patient with AF (17). The AFEQT is a self-reported questionnaire with responses on a 7-point Likert scale. The 20-item instrument is divided into three domains (4-item symptom score, 8-item daily activities score, 6-item treatment concerns score) plus two treatment satisfaction questions. The domains symptoms, daily activities and treatment can be aggregated into an overall score.

The AFEQT has been developed as a self-administered questionnaire for patients with AF. Reading and understanding the questionnaire in the applied language is mandatory when completing the instrument (18). The AFEQT questionnaires should preferably be signed off by the patient, but if it is not possible to obtain the signature of the patient, it is accepted that a member of the site study team signs and dates the questionnaire to confirm their validity. If the questionnaire is administered by phone, the person conducting the follow up call should sign off the questionnaire.

The validated languages cover the following: French, German, Italian, Spanish (Spain), Polish and Dutch, Korean. The AFEQT questionnaire will be applied to all patients, either in the linguistically validated country-specific version or, if a country-specific validated version does not exist, in the not validated version translated into the local language of the respective patients according to local requirements and regulations. To avoid possible confounders, all analyses regarding the AFEQT questionnaire will be performed for the overall sample and stratified by validated vs not validated version.

This also applies to the mode of questionnaire administration: In general, the AFEQT questionnaire will be filled in by the patient himself. However, in some sites the AFEQT questionnaire will be administered by telephone interview. To avoid possible confounders, all analyses regarding the AFEQT questionnaire will be performed for the overall sample and stratified by self-administered vs administered by telephone interview.

The license for using the questionnaire in local languages of participating countries will be obtained and submitted under the request.

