## 6.3 Quality of Life Questionnaires

In this registry, QoL will be assessed with the *Atrial Fibrillation Effect on Quality of Life* (AFEQT) questionnaire. It is a standardized, disease-specific, reliable and responsive measure of health-related QoL in patients with atrial fibrillation. The AFEQT is a self-reported

questionnaire with responses on a 7-point Likert scale. The 20-item instrument is divided into three domains (a 4-item Symptom score, an 8-item Daily Activities score, a 6-item Treatment Concerns score) plus two Treatment Satisfaction questions. The domains Symptoms, Daily Activities and Treatment can be aggregated into an overall score.

For all questionnaires, the frequencies of the given answers are presented by country and overall. If - based on the answers – scores are constructed these are presented, too.

The AFEQT questionnaire consists of 3 functional subscales (Symptoms [4 items], Daily Activities [8 items], Treatment Concern [6 items]) that are part of the overall AFEQT score. The 2 questions on Treatment Satisfaction are computed as its own subscale similarly to the overall score.

- Symptoms [*not at all bother OR I did not have this symptom; hardly bothered; a little bothered; moderately bothered; quite a bit bothered; very bothered; extremely bothered*]:
  - Palpitations: Heart fluttering, skipping or racing
  - Irregular heartbeats
  - Pause in heart activity
  - Light-headedness or dizziness
- Daily Activities:
  - Ability to have recreational pastimes, sports, and hobbies  
[*not at all limited; hardly limited; a little limited; moderately limited; quite a bit limited; very limited; extremely limited*]
  - Ability to have a relationship and do things with friends and family  
[*not at all limited; hardly limited; a little limited; moderately limited; quite a bit limited; very limited; extremely limited*]
  - Doing any activity because you felt tired, fatigued, or low on energy  
[*no difficulty at all; hardly any difficulty; a little difficulty; moderately difficulty; quite a bit of difficulty; a lot of difficulty; extreme difficulty*]
  - Doing physical activity because of shortness of breath  
[*no difficulty at all; hardly any difficulty; a little difficulty; moderately difficulty; quite a bit of difficulty; a lot of difficulty; extreme difficulty*]
  - Exercising  

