[*no difficulty at all; hardly any difficulty; a little difficulty; moderately difficulty; quite a bit of difficulty; a lot of difficulty; extreme difficulty*]
  - Walking briskly  
[*no difficulty at all; hardly any difficulty; a little difficulty; moderately difficulty; quite a bit of difficulty; a lot of difficulty; extreme difficulty*]
  - Walking briskly uphill or carrying groceries or other items, up a flight of stairs without stopping  
[*no difficulty at all; hardly any difficulty; a little difficulty; moderately difficulty; quite a bit of difficulty; a lot of difficulty; extreme difficulty*]
  - Doing vigorous activities such as lifting or moving heavy furniture, running, or participating in strenuous sports like tennis or racquetball  
[*no difficulty at all; hardly any difficulty; a little difficulty; moderately difficulty; quite a bit of difficulty; a lot of difficulty; extreme difficulty*]
- Treatment Concern [*not at all bother; hardly bothered; a little bothered; moderately bothered; quite a bit bothered; very bothered; extremely bothered*]:

- Feeling worried or anxious that your atrial fibrillation can start anytime
- Feeling worried that atrial fibrillation may worsen other medical conditions in the long run
- Worrying about the treatment side effects from medication
- Worrying about complications or side effects from procedures like catheter ablation, surgery, or pacemaker therapy
- Worrying about side effects of blood thinners such as nosebleeds, bleeding gums when brushing teeth, heavy bleeding from cuts, or bruising
- Worrying or feeling anxious that your treatment interferes with your daily activities
- Treatment Satisfaction [*extremely satisfied; very satisfied; somewhat satisfied; mixed with satisfied and dissatisfied; somewhat dissatisfied; very dissatisfied; extremely dissatisfied*]:
  - How well your current treatment controls your atrial fibrillation
  - The extent to which treatment has relieved your symptoms of atrial fibrillation

For the scoring of the AFEQT, see chapter 7.4.3 in the SAP.

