### Overall AFEQT score

In a first step, the levels of the 7 answer categories (equal to the order of appearance) for the 20 questions contributing to the Symptom subscale (i.e. questions 1 to 20) are coded as follows:

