**(d) Questions 19 to 20:**

level 1 ( extremely satisfied )	→ 1
level 2 ( very satisfied )	→ 2
level 3 ( somewhat satisfied )	→ 3
level 4 ( mixed with satisfied and dissatisfied )	→ 4
level 5 ( somewhat dissatisfied )	→ 5
level 6 ( very dissatisfied )	→ 6
level 7 ( extremely dissatisfied )	→ 7

In a second step, using the assigned values the Overall AFEQT score is calculated as follows:

$$100 - \left[ \frac{(\text{sum of severity for all questions answered} - \text{number of questions answered}) \times 100}{(\text{total number questions answered} \times 6)} \right]$$

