### 8.3.5 Evaluate QoL (AFEQT) dynamic at 12 month FU

Quality of Life analysis will be done for all available subjects. Therefore, completed AFEQT questionnaire at baseline and at 12 month FU will be used. With it, single scales and AFEQT score will be analysed at baseline and at 12 months. Also, absolute and relative differences in AFEQT score between baseline and 12 months will be displayed. Score calculations are described in SAP chapter 7.4.3, rules for analysis in SAP chapter 6.3.

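### SAP 7.4.3 scores the overall AFEQT on 20 items although SAP 6.3 and CIP 3.5 define it on 18; SAP 6.3.1 also makes the CIP's stratified AFEQT reporting conditional on p-values

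*SAP*

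**What the plan says.** **Definition of the overall score.** CIP 3.5 describes a 20-item instrument with three domains (4, 8 and 6 items) plus two satisfaction questions, and states: "The domains symptoms, daily activities and treatment can be aggregated into an overall score". SAP 6.3 repeats this. It lists Symptoms with 4 items and then "Daily Activities [8 items], Treatment Concern [6 items]) that are part of the overall AFEQT score". Of the remaining two items it says: "The 2 questions on Treatment Satisfaction are computed as its own subscale similarly to the overall score".

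**Scoring rule.** In SAP 7.4.3, under Overall AFEQT score, the answer levels "for the 20 questions contributing to the Symptom subscale (i.e. questions 1 to 20) are coded as follows". The coding blocks run through to block (d), questions 19 and 20, and the formula starts from the "sum of severity for all questions answered". Both places that use the score point here. SAP 6.3 ends with "For the scoring of the AFEQT, see chapter 7.4.3 in the SAP", and SAP 8.3.5, the QoL objective, says "Score calculations are described in SAP chapter 7.4.3, rules for analysis in SAP chapter 6.3".

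**Reporting rule.** CIP 3.5 says that "all analyses regarding the AFEQT questionnaire will be performed for the overall sample and stratified by validated vs not validated version", and makes the same commitment for self-administered against telephone completion. Neither carries a condition. SAP 6.3.1 instead sets out two sequential two-tailed Wilcoxon-Mann-Whitney tests at p<0.05, first on language version and then on mode, and their results determine which data are dropped, merged or separated.

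**The concern.** The 12-month change in AFEQT is a named ancillary objective. A programmer who follows SAP 7.4.3 will produce a headline score that mixes treatment satisfaction into a quantity defined on symptoms, daily activities and treatment concern. Satisfaction with treatment may well move differently from the other domains after an ablation, so the resulting error can go either way and cannot be signed in advance.

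The secondary issue is that a significance test takes the place of a reporting commitment. SAP 6.3.1 assumes that the language groups have equal medical history and takes no confounders into account. A chance result or an ordinary case-mix difference between countries can therefore remove every non-validated language version from the QoL results, while a non-significant result does not show that the versions are equivalent.

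**Working it through.** **1. Item count.** From CIP 3.5 and SAP 6.3: 4 + 8 + 6 = 18. The figure 20 is reached only by adding the two satisfaction items (18 + 2 = 20). Neither document writes 18; it follows from the domain counts.

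**2. Relation between the two scores.** The SAP 7.4.3 formula for n answered items is

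score = 100 - (sum - n) x 100 / (6n).

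This is linear in the mean item level, so with all items answered

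score(20) = (18/20) x score(18) + (2/20) x satisfaction = 0.9 x score(18) + 0.1 x satisfaction.

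Check: items 1-18 at level 4 and items 19-20 at level 1 give a sum of 72 + 2 = 74, and 100 - (74 - 20) x 100/120 = 55. The relation gives 0.9 x 50 + 0.1 x 100 = 55.

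**3. Error.** At one visit the error is 0.1 x (satisfaction - score(18)), which lies between -10 and +10 points. In the change from baseline it is 0.1 x (satisfaction change - 18-item change), with arithmetic limits of -20 and +20. It is zero only when both change by the same amount.

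**4. Illustration (levels assumed, not from the documents).** Items 1-18 move from level 3 (score 66.67) to level 2 (83.33), an 18-item change of 16.67.

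| Satisfaction level | 20-item baseline | 20-item at 12 months | Change | Error |
|---|---|---|---|---|
| 3 to 3 | 66.67 | 81.67 | 15.00 | -1.67 |
| 3 to 2 | 66.67 | 83.33 | 16.67 | 0.00 |
| 4 to 2 | 65.00 | 83.33 | 18.33 | +1.67 |

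**5. Branches of SAP 6.3.1 against CIP 3.5.** The CIP asks for the overall sample and both sets of strata.

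| Test result | What SAP 6.3.1 does | Missing relative to CIP 3.5 |
|---|---|---|
| Language significant (Scenario 1) | Drops all non-validated versions; no mode rule given | Full overall sample, language strata, mode strata |
| Language not significant (Scenario 2) | Pools languages, goes to the mode test | Language strata |
| Then mode significant (Scenario 3) | Analyses modes separately, does not merge them | Overall result, language strata |
| Then mode not significant (Scenario 4) | Merges everything | Both sets of strata |

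No branch delivers the CIP's set of results. SAP Appendices C and D list no language or mode stratum that would restore it.

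**6. Chance of triggering.** With no true difference and one score tested, step 1 excludes the non-validated data 5% of the time. If the two tests are independent, at least one triggers with probability 1 - 0.95 x 0.95 = 9.75%.

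**The case against.** **On scoring.** The mention of the Symptom subscale in the Overall block is plainly a copying slip, and one could suppose that the 20 is a slip too. It is not confined to the label: the item range, block (d) and the formula all cover questions 19-20. A fairer objection is that the two definitions are general descriptions, whereas 7.4.3 is an explicit algorithm. The instrument's scoring manual, cited in the CIP's reference list, would settle the matter and is not among the documents. That stands to this extent: the documents prove a contradiction, and their own definitions favour 18. The fix must therefore leave room for a deliberate 20-item score. The effect is also modest in the illustration, the single scales are reported anyway under SAP 8.3.5, and the score can be recomputed from the items.

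**On the tests.** CIP 4.4 lets the SAP change analysis methods without an amendment unless objectives change, provided that the SAP describes and justifies the change. SAP 6.3.1 describes its procedure fully, gives a data-quality purpose and states its equal-history assumption openly. But it does not say that it supersedes CIP 3.5 or why. Elsewhere the SAP does announce such departures (follow-up windows in 7.2.3, the AF recurrence definition in 8.1.1).

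SAP 7.2.3 combines visit and phone data only for listed variable groups, AFEQT not among them, and shows non-combinable information separately. This might seem to protect the mode contrast, but Scenario 4 is specific to AFEQT and merges the modes.

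The non-validated languages largely match five participating countries (Georgia, Greece, Hungary, Israel, Portugal). If data are pooled, the by-country output in SAP 6.3, 8 and 8.7 therefore keeps much of the language contrast visible. It does not restore excluded data or show mode.

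**Stronger readings to avoid.** A reader might infer a fixed size of difference that triggers exclusion. Assuming 400-1000 respondents, 10-36% on non-validated versions and normal scores, it would be roughly 0.13 to 0.33 SD. The documents give no counts by language, and a rank test is not a fixed function of the SD difference, so no such figure is relied on here. A reader might also infer that the registry's main result is compromised. Nothing supports that, because AFEQT does not enter the 12-month success estimate or safety.

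**Conclusion.** The scoring rule is wrong as written against the plan's own definition in both documents. The formula for the error is exact when all items are answered; the -1.7 to +1.7 points rest on assumed response levels. The documents give no threshold of relevance for AFEQT against which to judge that size. The scoring error is confined to the overall score.

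The secondary point also holds: the CIP's unconditional overall-plus-stratified reporting has been replaced by significance gates, with no statement that CIP 3.5 is superseded. The most serious consequence is exclusion of data by p-value. The 5% is a property of the test with no true difference; the probability under real case-mix differences cannot be computed from the documents.

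This should be corrected before the final analysis, but it touches an ancillary objective only.

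**What to change.** **SAP 7.4.3.** Limit the overall score to questions 1-18, with the denominator equal to the number of items answered among those 18, times 6. Use questions 19-20 only in the satisfaction subscale. Correct the copied Symptom subscale labels in the Treatment Concern, Treatment Satisfaction and Overall blocks. If a 20-item score is intended, say so, justify it and change SAP 6.3 to match.

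**SAP 6.3.1.** Report AFEQT for the overall sample, by validated/not validated version and by self-administered/telephone mode, with no significance gate and no exclusion by p-value. Also state the mode stratum for questionnaires collected by site staff during hospital visits, which step 2 mentions without assigning.

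**Cost.** One scoring line, some SAP wording and a few additional stratified tables. No new data are needed for the scoring change, since the items are coded individually.

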#### **(a) Questions 1 to 4:**

level 1 ( not at all bothered OR I did not have this symptom )	→ 1
level 2 ( hardly bothered )	→ 2
level 3 ( a little bothered )	→ 3
level 4 ( moderately bothered )	→ 4
level 5 ( quite a bit bothered )	→ 5
level 6 ( very bothered )	→ 6
level 7 ( extremely bothered )	→ 7

#### **(b) Questions 5 to 6:**

level 1 ( not at all limited )	→ 1
level 2 ( hardly limited )	→ 2
level 3 ( a little limited )	→ 3
level 4 ( moderately limited )	→ 4
level 5 ( quite a bit limited )	→ 5
level 6 ( very limited )	→ 6
level 7 ( extremely limited )	→ 7

#### **(b) Questions 7 to 12:**

level 1 ( no difficulty at all )	→ 1
---	-----

level 2 ( hardly any difficulty )	→ 2
level 3 ( a little difficulty )	→ 3
level 4 ( moderate difficulty )	→ 4
level 5 ( quite a bit of difficulty )	→ 5
level 6 ( a lot of difficulty )	→ 6
level 7 ( extreme difficulty )	→ 7

**(c) Questions 13 to 18:**

level 1 ( not at all bothered )	→ 1
level 2 ( hardly bothered )	→ 2
level 3 ( a little bothered )	→ 3
level 4 ( moderately bothered )	→ 4
level 5 ( quite a bit bothered )	→ 5
level 6 ( very bothered )	→ 6
level 7 ( extremely bothered )	→ 7

**(d) Questions 19 to 20:**

level 1 ( extremely satisfied )	→ 1
level 2 ( very satisfied )	→ 2
level 3 ( somewhat satisfied )	→ 3
level 4 ( mixed with satisfied and dissatisfied )	→ 4
level 5 ( somewhat dissatisfied )	→ 5
level 6 ( very dissatisfied )	→ 6
level 7 ( extremely dissatisfied )	→ 7

In a second step, using the assigned values the Overall AFEQT score is calculated as follows:

$$100 - \left[ \frac{(\text{sum of severity for all questions answered} - \text{number of questions answered}) \times 100}{(\text{total number questions answered} \times 6)} \right]$$

## 7.5 Replacement of Data

### 7.5.1 Replacement of missing values

All reasonable attempts will be undertaken to ensure completeness of data collection in this registry. Before database lock, as many queries as possible will be cleared. If Note to

Files arises after database closure (baseline data base lock or final database lock) that relate to data analysis, the data is changed accordingly for analysis.

According to the Clinical Investigational Plan, missing values will not be replaced for any of the parameters in the statistical analysis. Only observed cases will be evaluated.

### 7.5.2 Replacement of outliers

In general, outliers are evaluated as reported. In the event of highly implausible values (in the sense of extreme outliers) documented in the database after completion of data validation the following approach is used:

For some baseline variables (e.g. age, weight, height) as well as for vital signs so-called plausibility ranges will be defined (Table 3).

Observed values that are not within these ranges are set to missing within the analysis datasets. The intention of these ranges is to set them as wide as possible, so that only values that are obviously impossible (e.g. age of 150 years or systolic blood pressure of 20 mmHg) are set to missing. Borderline values confirmed by the investigator within a query will not be set to missing.

The definition of the ranges is always set in consultation with a medical expert. An appropriate documentation of the implausibility ranges is given in the following table of this SAP according to the ranges in the Data Validation Plan.

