#### Relative pre-post differences

Relative pre-post differences (also called percent changes) will always be calculated as  $100\% \text{ (post-baseline value minus baseline value) / baseline value}$ .

Pre-post differences will be calculated for the following variables (other can be proposed retrospectively):

**Table 2:** Variables for pre-post differences

Variables	Pre- value	Post- value	Derived variables
Antiarrhythmic medication Anticoagulation medication Antiplatelets Other cardiovascular medication	Discharge	12MFU visit/ 12MFU by phone	Number of patients 
 
• Never on
 
• Newly on
 
• Continued
 
• Discontinued
 

AFEQT-Score	Baseline	12MFU/ 12MFU by phone	Absolute change in AFEQT score
AF burden	Baseline	12MFU visit/ 12MFU by phone	Absolute change in AF burden [%]
EHRA AF symptoms classification	Baseline	12MFU visit/ 12MFU by phone	

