# 8 Descriptive Statistics

This section describes the most relevant parts of the statistical analyses planned for this registry. All planned statistical methods will be described in detail in the Statistical Analysis Plan, which should be finalized prior to interim analysis and need to be finalized prior final analysis.

In general, this registry is intended to collect data under real life conditions. The statistical analysis will be performed in explorative and descriptive manner, i.e. no pre-specified hypothesis testing.

All variables collected in the CRF as well as the data obtained from the QoL assessments and all derived parameters will be used in the statistical analysis.

Binary, categorical, and ordinal parameters will be summarized by means of absolute and percentage numbers within the various categories.

Continuous data will be summarized by means of standard statistics, i.e. number of available data, number of missing data, mean, standard deviation, minimum, median, maximum, 5th and 95th percentile, lower and upper quartile (see SAP Appendix A).

Time-to-event data is planned to be analysed via a Cox proportional hazard regression model presenting hazard ratios and the corresponding 95% CI. In addition, Kaplan-Meier

curves may be presented for the time-to-event data. Two-sided 95%-CI will be presented for important parameters, but should be interpreted in an exploratory descriptive way. No formal statistical tests are planned within the statistical analysis. Event rates will be calculated for 3, 6, 9 and 12 months after first documented procedure and may be displayed graphically.

To measure statistical differences in continuous or dichotomous/ multinomial variables between baseline and 12 month FU non-parametric (e.g. Friedman's Chi-Square Test, McNemar's Test) will be utilized. The test is only performed if the variable is not missing at admission and discharge.

A biometrical report including descriptive statistics of all relevant documented parameters will be generated for the overall patient population as well as for each participating country (SAP chapter 8.7). Depending on the variable(s) of interest, additional selection criteria for subjects (e.g. subgroup analyses) considered in specific analyses may be used, if considered useful during the statistical analysis (SAP chapter 8.6).

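### SAP Table 3 gives LVEF two unlabelled plausibility ranges, 15-70% and 0-100%; the narrower one can set plausible values to missing and, if it is the baseline rule, could lower the baseline LVEF summary

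*SAP*

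**What the plan says.** SAP section 7.5.2 (Replacement of outliers) starts from the position that outliers are analysed as reported. For highly implausible values still present after data validation it sets plausibility ranges, with this consequence: "Observed values that are not within these ranges are set to missing within the analysis datasets". The limits are intended to be generous, and the stated purpose reads: "so that only values that are obviously impossible (e.g. age of 150 years or systolic blood pressure of 20 mmHg) are set to missing". There is one exemption: "Borderline values confirmed by the investigator within a query will not be set to missing".

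Table 3 of that section has two rows for documented LVEF:

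- **First row, 15-70%.** It sits among height, weight, age, earlier ablations, AF burden and left atrial diameter.
- **Second row, 0-100%.** It comes after the procedure-time and per-vein rows, next to a further set of cardioversion counts.

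No row of Table 3 carries a form or visit label, and no reason is given for the difference.

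Deleted values are not replaced. SAP section 7.5.1 says "Only observed cases will be evaluated". SAP section 8 plans non-parametric methods, introduced with the words "To measure statistical differences in continuous or dichotomous/ multinomial variables between baseline and 12 month FU", and limits them to patients with both values present.

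**The concern.** One variable has two deletion rules, and the table does not tell the programmer which rule belongs to which form. The narrower rule also fails the SAP's own standard. An LVEF of 72% or 12% cannot be obviously impossible if another row of the same table accepts it.

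If the first row applies to baseline and the second to follow-up, the two visits are cleaned asymmetrically. Baseline LVEF would be cut at the top and follow-up LVEF would not. Two things could follow:

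- The baseline LVEF summary could be too low. SAP Appendix B tabulates diagnostics at baseline for the BAS, FAS and EFAS, and the benchmark reports in SAP section 8.7 cover all baseline parameters.
- A comparison of baseline with follow-up could show a small rise without any true change. In unpaired tables this comes straight from the truncation. In paired data it is regression to the mean, because the retained patients were selected for not having a high baseline value.

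**Working it through.** The plan gives no figure for LVEF change, so there is nothing to reproduce. The question is how large the artefact could be.

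**Inputs from the SAP.** Ranges 15-70% and 0-100% (Table 3); set-to-missing rule and query exemption (section 7.5.2); complete pairs only (section 8).

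**Assumptions, not in the documents.**
- LVEF is normal with mean m = 57-62 and SD s = 7-9, the same at both visits (no true change).
- Correlation between visits is r = 0.5-0.7.
- The first row is the baseline rule and the second the follow-up rule.
- Values are whole percentages, so 70 is kept and 71 deleted. The cut is c = 70.5.
- No out-of-range value is rescued by a query.

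**Formulas.** With z = (c - m)/s, and φ and Φ the standard normal density and distribution function:
- share deleted = 1 - Φ(z)
- fall in baseline mean = s × φ(z)/Φ(z)
- apparent paired change = (1 - r) × fall in baseline mean

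The lower limit of 15 is ignored here because it removes almost nothing at these means.

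**Smallest case, m = 57, s = 7.**
- z = 13.5/7 = 1.929; Φ = 0.9731; φ = 0.0621
- deleted: 2.7%
- fall: 7 × 0.0621/0.9731 = 0.45 points
- paired change at r = 0.7: 0.3 × 0.447 = 0.13 points

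**Largest case, m = 62, s = 9.**
- z = 8.5/9 = 0.944; Φ = 0.8275; φ = 0.2554
- deleted: 17.2%
- fall: 9 × 0.2554/0.8275 = 2.78 points
- paired change at r = 0.5: 0.5 × 2.78 = 1.39 points

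**Dependence on the correlation.** The factor (1 - r) is zero at r = 1.0. A simulation with the cut at exactly 70 (mean 55-60, SD 8-10) gave a paired mean change of 0.29 to 1.44 points at r = 0.5, 0.17 to 0.87 at 0.7, 0.06 to 0.28 at 0.9 and 0.00 at 1.0. Median changes were close to the means (1.37 against 1.44 in the largest setting), so using non-parametric tests does not remove the effect.

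**Dependence on the mean.** In unpaired summaries with the cut at 70 and SD 6-12, the apparent rise is 0.00 to 0.35 points at mean 45, 0.1 to 2.4 at mean 55 and 0.6 to 4.2 at mean 60. Below a mean of 42.5, the midpoint of 15 and 70, the sign reverses: -0.33 points at mean 40, SD 12.

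**Lower tail.** Under 0.05% of values fall below 15% at mean 55 or 60 with SD up to 12.

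**The case against.** The strongest reply is that deletion is not automatic. The rule applies only after data validation, and a borderline value that the investigator confirms is kept, so a confirmed 72% could survive. This stands. It makes the figures above upper bounds under the stated assumptions, and any share of values that is queried and confirmed lowers them. It does not settle the matter: borderline is not defined, and the SAP does not show whether a 72% would trigger a query, because that depends on a Data Validation Plan that is not among the documents.

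Second, the baseline and follow-up reading is an inference from row order. This also stands, although the neighbouring rows make it the natural reading. If it is wrong, there are still two unlabelled rules for one variable.

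Third, little rests on LVEF. It is not among the pre-post variables of SAP Table 2, although that list is open to later additions. It does not appear in the objectives, the predefined graphs, the subgroups or the comparison groups. The protocol requires no extra tests (section 6.2) and allows the 12-month contact by phone (section 3.4), so follow-up LVEF need not exist for every patient. All of this stands and limits the consequence.

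Fourth, the SAP's test uses complete pairs. A patient with 72% at both visits therefore leaves the comparison and does not appear as a riser. What remains is the smaller regression effect calculated above.

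**Conclusion.** The inconsistency holds and can be seen on the page. Table 3 has two LVEF ranges without labels, and the 15-70% row can remove plausible unconfirmed values, contrary to the aim stated in section 7.5.2.

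The numerical consequence is conditional. If the rows are baseline and follow-up and no value is rescued by query, an assumed mean of 57-62 and SD of 7-9 give 2.7-17.2% of baseline values deleted and a baseline mean lower by 0.45-2.8 points. The paired artefact is 0.13-1.4 points at correlation 0.5-0.7.

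A reader might infer more than the documents support:

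- **That LVEF will appear to rise after ablation.** The size and sign depend on a distribution and a correlation that the documents do not give. The effect is negligible at mean 45 with a small SD, reverses below 42.5, and vanishes in pairs at correlation 1.0.
- **That the registry would report improved ventricular function.** No such analysis is specified.
- **That patients below 15% are materially lost.** At the assumed means almost none lie there.

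No study objective is affected. This is a minor correction to descriptive tables and to any exploratory LVEF comparison.

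**What to change.** In SAP Table 3, label each row with the form it applies to. Use one common wide LVEF range on all forms, for example the 0-100% row that is already there. State that an LVEF value is set to missing only if it lies outside that range and has not been confirmed by query. If the sponsor has a reason for a narrower range on one form, the SAP should state it.

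The cost is one table cell, the row labels and one line of the derivation program. No new data are needed.
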